Another recent study, by Tvetenstrand CD et al.⁶ was conducted in a hospital with ambulatory abdominal surgery patients with DSUVIA dosed 30 minutes prior to induction. A total of 47 patients were in the DSUVIA arm and 81 matched historical controls were compared. This study showed a decrease in overall IV opioid requirements and a decreased Phase 1 PACU time. No patients required naloxone for respiratory depression in either group.

Sufentanil is a drug with a rapid onset (15 min) and high potency (30 mg= morphine 5mg) (pka = 8.0 and solubility coefficient greater than 2000). It is highly bioavailable and highly lipophilic with a high therapeutic opioid index (LD50/ED50). It has a much lower Cmax compared with IV sufentanil. It reaches 70 % Cmax in 30 minutes, lasting as long as 3 hours. Based on existing outcomes data, we hypothesize that there will be a clinically significant difference in spine surgery patients as compared to the historical controls.

Purpose:

In this study we plan to examine the perioperative use of Dsuvia (sufentanil SL; FDA approval 2018) in the analgesic regimen for spine surgery, one of the most common surgeries performed in the US. Patients undergoing spinal fusion surgery often experience significant pain during the first three postoperative days⁷. Currently, no data are available for this patient population which routinely experiences moderate to severe acute pain requiring significant opioid use. We will analyze whether Dsuvia (sufentanil SL) is associated with lower pain scores, frequency of rescue

opioids, lower overall opioid consumption, PACU and hospital length of stay, and side effects of opioid use (i.e., nausea, vomiting, constipation, respiratory effects).

Hypotheses:

1. The perioperative use of Dsuvia 30 mcg SL in a prospectively recruited cohort of patients undergoing spine surgery will be associated with lower postoperative numeric rating scale pain scores (NRS; primary outcome) than observed in two historical control groups that did not receive Dsuvia: one group that received intraoperative remifentanil infusion and one that received intraoperative sufentanil infusion.

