2. The perioperative use of Dsuvia (sufentanil SL) will be associated with lower overall opioid consumption, lower frequency of rescue opioids, lower PACU and hospital length of stay, and fewer side effects of opioid use (i.e., nausea, vomiting, constipation, respiratory complications) than observed in two historical control groups of patients receiving remifentanil or sufentanil infusions without perioperative Dsuvia.

Methods:

The study design is an Observational Longitudinal (OL) study with historical controls. There will be 1 prospectively recruited study arm (patients receiving the study drug Dsuvia) and 2 historical control arms (one that received an intraoperative remifentanil infusion and the other that received an intraoperative sufentanil infusion, both without Dsuvia).

Inclusion criteria:

[figure not shown]
Patients undergoing spine surgery (1-3 levels) who are opioid-naïve (no opioid use 30 days prior to surgery), 18-75 years old, ASA physical status 1-3.

Exclusion criteria:

Microdiscectomy, chronic opioid users, significant respiratory depression, acute or severe bronchial asthma, chronic lung disease, known or suspected gastrointestinal obstruction including paralytic ileus, liver disease (defined as alkaline phosphatase (ALP) > 56, aspartate aminotransferase (AST) > 100), known allergy or hypersensitivity to sufentanil or its components, baseline dementia, serotonin syndrome, adrenal insufficiency, severe hypotension, increased intracranial pressure, brain tumors, head injury, impaired consciousness, malignant hyperthermia, ASA physical status > 3, age > 75, pregnant patients.

IV. STUDY SCHEMA:

Patients undergoing spine surgery (1 or more levels)

Dsuvia 30mcg SL

Intraoperative Phase

General endotracheal anesthesia (TIVA with propofol/sufentanil)

Standardized anesthetic technique (see protocol below)

Dsuvia x1 prior to emergence from anesthesia

Postoperative Phase

Pain scores (NRS) q15 min up to 2 hrs

Concomitant Medication use/opioid consumption

Dsuvia prn q1hr as 1st line (NRS >3); Fentanyl prn as 2nd line, or 1st

line if repeat Dsuvia cannot yet be given and NRS is >3 (see PACU schema below)

Up to 3 doses of Dsuvia may be administered in the PACU (each at least 1 hr apart)

Hospitalization Phase

Follow up during inpatient hospital stay

Concomitant Medication use/pain scores

Both arms: standard of care analgesia (PO and IV prn)

Quality of Recovery (QoR); patient satisfaction (study arm only)

Post-discharge Phase

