Follow up following discharge

Prescription opioid use

Outcomes:

Primary:

Mean postoperative pain scores (PACU)

Secondary:

Mean postoperative pain scores (inpatient)

opioid consumption (MMEs, PACU and inpatient)

Frequency of opioid rescue medications given

PACU LOS (min)

hospital LOS (days)

nausea, vomiting, constipation, respiratory events

sedation level (PACU)

quality of recovery (QoR 15)

utilization of prescription opioids following discharge

As shown above, the following secondary outcomes will also be collected in the Study cohort to obtain estimates that can be used to power future randomized controlled trials: sedation level, quality of recovery (QoR-15)⁸, patient satisfaction score (satisfaction with the level of pain control, 6-point scale⁴), and utilization of prescription opioids following discharge.

Safety assessments will include adverse events (AEs) and use of concomitant medications, periodic monitoring of vital signs (blood pressure, heart rate, and respiratory rate), and continuous monitoring of oxygen saturation in the PACU.

Detailed Clinical Protocol

Preoperative:

The surgeon will approach the patient and introduce the study and one of the investigators will explain the study to the patient. The surgeon will assess subject at their visit. At this visit, the surgeons will identify any patients that may benefit from Dsuvia. The information will be provided to one of the investigators. The investigator will subsequently review their eligibility and inclusion criteria. If the subject continues to meet all the criteria, the investigator will explain the study with the patient. Thereafter the patients will be provided the consent forms for their review and a 24/7 contact number for any questions regarding this study. All patient questions will be answered and informed consent will be obtained by one of the investigators who is a licensed physician listed on the protocol. The patient will be provided contact information. A co-investigator will be available to answer

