- If at any time the patient's NRS >3 after 20 min following an administration of either Dsuvia or fentanyl, the patient can receive a repeat dose of fentanyl until again eligible to receive Dsuvia.

Once the patient is transferred to the floor, both groups will receive the standard of care postoperative pain management orders (ie PO and IV prn analgesia for NRS > 3).

Patients who require additional doses of Dsuvia will be monitored for respiratory depression for at least one hour after the last administration of the drug dose.

Sample Size/Statistical analysis:

The primary outcome is nurse-collected mean pain scores. Assuming a within-group standard deviation in PACU NRS pain score of 2.5 points⁷, enrollment of 30 patients in the study group and inclusion of at least 80 patients in each retrospective control group will provide at least 80% power at a two sided alpha level of 0.025 (0.05/2 pair-wise comparisons) to detect a minimal clinically important difference of 2 points⁹ between the Study group and each of the retrospective groups using linear regression.

To account for any potential lack of comparability in baseline characteristics between patients in the Study and retrospective groups, all outcomes will be compared between the prospective group and each of the retrospective groups using doubly robust estimation incorporating both multivariable linear regression adjustment and inverse probability of treatment weights based on the propensity score¹⁰. Doubly robust estimation will allow for unbiased treatment effect estimates even if one of the two models (i.e., propensity score model or outcome model) is miss-specified. The multivariable linear regression models for the outcomes will adjust for the following covariates: age, sex, BMI, ASA class, surgical invasiveness tier, reoperation, history of anxiety, anxiolytic use, history of depression, and antidepressant use. Analytic weights will be based on the inverse of the propensity score, calculated via logistic regression as the probability of being in the Dsuvia group conditional upon the aforementioned covariates included in the multivariable outcome model.

Investigator Name/Institution:

[name], MS
Associate Professor of Anaesthesia
Director, Neuroanesthesia

Brigham and Women's Hospital
Harvard Medical School
Department of Anesthesiology, Perioperative and Pain Medicine
[name]
[name]
[contact]
Email: [contact]

Senior Project Manager:
[name]
Email: [contact]

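### The liver-disease exclusion gives ALP and AST limits with no units and no 'and' or 'or'; if ALP is in U/L, neither reading separates liver disease from health

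*Combined protocol and SAP*

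**What the plan says.** All references are to the combined protocol and SAP.

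- **Methods, Exclusion criteria.** One item in a comma-separated list reads "liver disease (defined as alkaline phosphatase (ALP) > 56, aspartate aminotransferase (AST) > 100". A comma joins the two limits. There is no unit, laboratory range or multiple of an upper limit.
- **Methods, Inclusion criteria.** The population is "Patients undergoing spine surgery (1-3 levels) who are opioid-naïve (no opioid use 30 days prior to surgery), 18-75 years old, ASA physical status 1-3".
- **Detailed Clinical Protocol, Preoperative.** After the surgeon identifies a candidate, "The investigator will subsequently review their eligibility and inclusion criteria". The section describes no liver blood test and does not say when one is taken, although routine practice is to be followed.
- **Sample Size/Statistical analysis.** The plan is "enrollment of 30 patients in the study group and inclusion of at least 80 patients in each retrospective control group". Neither ALP nor AST is among the covariates of the outcome model or the propensity score. No screen-failure rate is given.
- **Historical controls.** The eligibility lists follow the description of all three arms. The document does not say whether the liver limits were applied to charts, or what happens when a chart has no liver panel.

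**The concern.** An exclusion defined by laboratory limits should tell the investigator, without guesswork, who is out, and those excluded should be the people the label describes. This one looks wrong on both counts. The ALP limit seems too low to mark disease if it is in U/L, and the missing connector changes who is excluded.

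Three things are at stake:

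- **Recruitment.** A literal 'either' reading could turn away a large share of healthy candidates.
- **Compliance.** If staff see the limit as implausible and pass over it, many of the 30 could be recorded as ineligible.
- **Who is studied.** The enrolled group would be restricted by a limit that does not identify liver disease. Under the 'both' reading, some patients with a raised AST would be admitted.

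**Working it through.** **1. The plan's own figure.** Inputs from Sample Size/Statistical analysis: "Assuming a within-group standard deviation in PACU NRS pain score of 2.5 points"; "at least 80% power at a two sided alpha level of 0.025 (0.05/2 pair-wise comparisons"; "to detect a minimal clinically important difference of 2 points"; groups of 30 and 80.

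- Standard error = 2.5 × √(1/30 + 1/80) = 0.535.
- Power ≈ Φ(2/0.535 − 2.241) = Φ(1.495) = 0.93.
- With the noncentral t distribution, power is 0.927 on 108 degrees of freedom and 0.926 on 98 (ten removed for covariates).

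The claim of at least 80% is reproduced. The ALP limit does not enter the calculation.

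**2. Reading A: either limit alone excludes, ALP in U/L.** The document gives no ALP distribution, so this step rests on assumptions. A reference interval (lo, hi) is taken as the central 95% of ALP in healthy adults, with either a normal or a log-normal shape.

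- Normal: m = (lo + hi)/2, s = (hi − lo)/3.92, P = 1 − Φ((56 − m)/s).
- Log-normal: the same formulas with ln(lo), ln(hi) and ln(56).
- Patients needed to enrol 30 = 30/(1 − P), calculated from unrounded P.

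The two extremes:

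- Interval 20–140, log-normal: m = (2.996 + 4.942)/2 = 3.969; s = (4.942 − 2.996)/3.92 = 0.496; ln 56 = 4.025; P = 1 − Φ(0.114) = 0.455; 30/(1 − P) = 55.
- Interval 44–147, normal: m = 95.5; s = 103/3.92 = 26.28; P = 1 − Φ(−1.503) = 0.934; 30/(1 − P) = 452.

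| Assumed interval (U/L) | Healthy adults above 56: normal | Log-normal | Otherwise eligible patients for 30 enrolled: normal / log-normal |
|---|---|---|---|
| 20–140 | 78.3% | 45.5% | 139 / 55 |
| 30–100 | 69.3% | 47.1% | 98 / 57 |
| 30–120 | 79.6% | 57.7% | 147 / 71 |
| 35–105 | 78.3% | 61.1% | 139 / 77 |
| 40–120 | 88.0% | 77.6% | 250 / 134 |
| 40–130 | 89.7% | 80.0% | 290 / 150 |
| 40–150 | 91.8% | 83.2% | 365 / 179 |
| 45–115 | 91.1% | 85.2% | 335 / 203 |
| 44–147 | 93.4% | 88.0% | 452 / 251 |

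The limit of 56 lies inside all nine intervals; the lowest upper limit tried is 100. The excluded share is above one half in 16 of 18 scenarios and slightly below it in two.

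**3. Reading A, limit ignored in practice.** With the same shares, 30 × 0.455 ≈ 14 to 30 × 0.934 ≈ 28 of the 30 enrolled patients would breach the written criterion.

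**4. Reading B: both limits must be exceeded.** A healthy candidate with ALP above 56 is now excluded only if AST is also above 100, so the shares in step 2 no longer apply. However, any patient with AST above 100 and ALP of 56 or less passes. No other exclusion in the list covers liver function.

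**The case against.** The strongest case against the point has four parts.

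- **The text does not say 'or'.** The comma leaves it open, and under 'and' the mass exclusion vanishes. This stands. A reader might infer that the rule as written excludes most healthy patients, but the document does not establish that. The figures in step 2 are conditional on 'or' and on U/L. The 'or' reading is the natural one in a list where each item excludes on its own, but it is still a reading. The objection does not rescue the criterion, because the 'and' reading has its own gap.
- **The reference interval comes from outside the document.** This also stands. Both the interval and the distribution are assumptions, and two of the 18 scenarios fall below one half, so even under 'or' a flat claim of 'most' is too strong. No candidate pool or accrual period is given either, so the screening counts show added burden and do not show that 30 cannot be reached.
- **Nothing shows harm to the comparison.** A reader might infer that the enrolled group would be unrepresentative in its pain response, or that the arms would be confounded because ALP is not adjusted for. The document supports neither. Nothing in it links ALP within the normal range to pain, opioid use or length of stay, and it does not say that controls escape the rule. The Purpose section describes the drug's use "in the analgesic regimen for spine surgery, one of the most common surgeries performed in the US", which says that the surgery is common and does not promise a representative sample.
- **Power is untouched.** Correct, as step 1 shows.

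What survives is narrower: a stated threshold that cannot be applied predictably and that gives a wrong result on either reading.

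**Conclusion.** The point holds in conditional form. If ALP is in U/L and either limit alone excludes, the rule does not separate liver disease from health. It would then exclude roughly 45.5% to 93.4% of healthy candidates and call for about 55 to 450 otherwise eligible patients to enrol 30. These figures rest on the assumed intervals and on normal or log-normal shapes in healthy adults; the distribution in this spine-surgery population is unknown. If both limits are required, those figures do not apply, and the defect becomes the admission of patients with AST above 100 whose ALP is 56 or less.

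The effect is on recruitment, eligibility compliance and who is studied. The stated power stands, and no bias in the primary pain comparison is shown. A comparability question would arise only if the limits were applied to the prospective arm and not to the controls, which the document leaves open. A reader might also infer a transcription error in the analyte or the number. That is a reason to check, and the document does not prove it.

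**What to change.** Before screening, the investigator should:

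1. Check the analyte and the value in the ALP limit, and the units of both limits, against the source used to draft the criterion and against the hospital laboratory's reference range, and correct whichever is wrong.
2. State both limits with units, or as multiples of the laboratory's upper limit.
3. Write 'and' or 'or' between them.
4. Say whether the rule also applies when historical controls are selected, and how a missing liver panel is handled, in controls and in the prospective arm.

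No replacement cut-off is proposed here; that is for the investigator and the laboratory.

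The cost is a one-line protocol amendment, plus a check of liver values already in the charts, where available, for the controls (at least 80 per group). If a missing panel were made a reason to exclude a control, the available pool would shrink, so that choice should be made before charts are pulled. The sample-size statement needs no change.

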questions on a 24 hour basis. It will be explained to the patient that they will be permitted to withdraw from the study at any time for any reason until their day of surgery. On arrival at the preoperative area, the patient will be assigned a code by one of the investigators. Prior to premedication, all patients will be made familiar with the use of numeric rating scale (NRS): 0-10 (no pain to the worst pain imaginable). The baseline NRS score will be recorded. All routine standard practices for surgery, anesthesia, and perioperative care will be followed with the exception of the study intervention. All patients will be premedicated with midazolam (0.025-0.05 mg/kg)

Intraoperative Management:

The Study arm will receive general endotracheal anesthesia (GETA). Anesthesia induction will be achieved with propofol (1.5-2.5mg/kg), succinylcholine (1mg/kg), and Fentanyl (50-100 mcg) bolus. Anesthesia maintenance will consist of TIVA (total intravenous anesthesia) with continued infusions of propofol (80-200 mcg/kg/min) and sufentanil (0.2-0.3mcg/kg/hr). The study group will receive Dsuvia 30 mcg at surgery end, administered by the anesthesiologist, timed to occur prior to emergence from anesthesia, and after the patient is turned supine. Antiemetic prophylaxis will be administered (ondansetron) per standard practice. The patient will then be transferred to the PACU.

Postoperative Management:

Note that Dsuvia will be ordered as q1hr prn, meaning that repeat doses must be administered at least 1 hr apart (up to 3 doses can be administered in the PACU).

Postoperative pain scores will be recorded by the PACU nurse and the research assistant. This will be obtained by using NRS scale every 15 mins up to 2 hours.

In the PACU, patients will be ordered to receive Dsuvia 30 mcg q1 hr prn for breakthrough pain (for NRS > 3) as the 1st line analgesic, with fentanyl as the rescue analgesic if the patient is still experiencing pain (NRS >3). The following opioid administration schema will be used for pain management in the PACU:

- 1st line: Dsuvia SL 30mcg (NRS >3). 2nd line: Fentanyl 25-50mcg (NRS >3)
- If upon arrival to the PACU the patient is still experiencing pain with NRS >3 but cannot yet receive a repeat dose of Dsuvia (because of having received 1st dose in the OR less than 1 hour ago), then the patient can receive fentanyl 25-50mcg prn until eligible to receive Dsuvia.

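### Hypothesis 2 claims lower overall opioid consumption, but the listed PACU-plus-inpatient MME outcome leaves out the operating-room Dsuvia tablet and all other intraoperative opioids

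*Combined protocol and SAP*

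**What the plan says.** **The claim.** The Purpose lists among its aims "opioids, lower overall opioid consumption, PACU and hospital length of stay". Hypothesis 2 says that perioperative Dsuvia "will be associated with lower overall opioid consumption, lower frequency of rescue opioids", compared with both historical control groups.

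**The outcome.** Under Outcomes, Secondary, the matching entry is "opioid consumption (MMEs, PACU and inpatient". Opioid use after discharge is listed separately and is described as collected in the study cohort.

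**Where opioids are recorded.** The Study Schema has separate Intraoperative, Postoperative, Hospitalization and Post-discharge phases. The line "Concomitant Medication use/opioid consumption" stands under the Postoperative Phase. The line "Follow up during inpatient hospital stay" stands under the Hospitalization Phase. The Intraoperative Phase has no line for collecting opioid amounts.

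**What is given before the PACU.** The schema's Intraoperative Phase includes "Dsuvia x1 prior to emergence from anesthesia", and Intraoperative Management repeats it: "The study group will receive Dsuvia 30 mcg at surgery end, administered by the anesthesiologist, timed to occur prior to emergence from anesthesia". The same section gives the study arm a fentanyl bolus at induction and a sufentanil infusion. Methods describes the two control groups as "one that received an intraoperative remifentanil infusion and the other that received an intraoperative sufentanil infusion, both without Dsuvia".

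**The concern.** The claim is wider than the measurement. The operating-room tablet is part of the exposure that Hypothesis 2 tests, it is given only in the study arm, and it comes just before the PACU window opens. The Background puts the duration of the sublingual product at up to 3 hours, so the tablet can still be acting while PACU consumption is counted.

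If the tablet simply takes the place of an opioid dose that would otherwise have been given in the PACU, the listed outcome falls although the patient's total has not. Reported under the wording of Hypothesis 2, that would read as a reduction in overall opioid use. At stake is what the trial may conclude about opioid sparing against either control group.

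The covariates under Sample Size/Statistical analysis include no intraoperative opioid dose. Adding one would not solve this, since adjustment cannot change what an outcome counts.

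**Working it through.** **1. The plan's own figure.** No effect size or power is stated for opioid consumption, so there is nothing to reproduce for this outcome. The one power statement concerns pain scores: 30 against 80 patients, SD 2.5, difference 2, two-sided alpha 0.025. The standard error is 2.5 × √(1/30 + 1/80) = 0.535, and 2/0.535 = 3.74. Subtracting the critical value 2.24 leaves about 1.50, which is 93% power by the normal approximation. That agrees with the stated minimum of 80%, and the present point does not touch it.

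**2. What the window contains.** Study-arm opioids, from Intraoperative Management and Postoperative Management:

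| Opioid | Place | Inside PACU plus inpatient? |
|---|---|---|
| Fentanyl 50–100 mcg at induction | Operating room | No |
| Sufentanil infusion 0.2–0.3 mcg/kg/hr | Operating room | No |
| Dsuvia 30 mcg, one tablet | Operating room | No |
| Dsuvia 30 mcg, up to 3 tablets as needed | PACU | Yes by timing, though the plan does not say it is counted |
| Fentanyl 25–50 mcg as needed | PACU | Yes |
| Any opioid within standard floor analgesia | Inpatient | Yes |

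**3. How the two quantities differ.** Let P be PACU plus inpatient MME and O intraoperative MME, with S for the study arm and C for a control group. Then:

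overall difference = (P_S − P_C) + (O_S − O_C)

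The listed outcome estimates only the first bracket. The second contains the tablet, the boluses and the infusions. For the controls the documents give only the type of infusion, with no rate, no duration and no account of boluses or end-of-surgery opioids. O_C is therefore unknown for both control groups, and so is the sign of the second bracket.

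**4. Pure substitution.** Suppose the tablet replaces a PACU dose of equal value m and nothing else changes. P_S falls by m and O_S rises by m. The listed outcome shows a saving of m; the overall change is −m + m = 0.

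**5. Size in counts, with no MME conversion.** With k PACU tablets, the operating-room tablet's share of a study patient's Dsuvia is 1/(1 + k):

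- k = 0: 1/1 = 100%
- k = 1: 1/2 = 50%
- k = 2: 1/3 = 33%
- k = 3: 1/4 = 25%

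The uncounted induction fentanyl equals between 50/50 = 1 and 100/25 = 4 single PACU fentanyl doses. These figures show how much study-arm opioid lies outside the window. They do not measure bias between groups.

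**The case against.** The strongest reply is that this is a matter of one adjective. The outcome states its window openly, and the tablet is openly specified as one per study patient. Asking what patients need after the intervention is a defensible question. In Hypothesis 2, overall stands next to the frequency of rescue opioids, so it could mean all opioids rather than rescue opioids alone, within the listed window. Neither overall nor inpatient is defined, so the exclusion of intraoperative opioids is inferred from the layout and is not stated.

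Much of this stands. The outcome is legitimate and should be kept, and the exclusion is indeed a reading. It is the natural reading, however. If inpatient meant the whole admission, naming the PACU beside it would be redundant. Pain scores are split in the same way, and the schema ties inpatient to the phase after the PACU. Hypothesis 1 says postoperative where it means that, whereas Hypothesis 2 concerns perioperative use and says overall. If the word was meant loosely, changing it costs almost nothing.

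A reader might also infer that the document holds several competing definitions of opioid consumption, because the Background speaks of other opioids and of IV requirements. That does not follow. Those phrases summarise earlier evidence. The plan's own Purpose, hypothesis and outcome list use one phrase and one outcome.

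**Conclusion.** The point holds as a mismatch between claim and outcome, and it should be fixed. PACU plus inpatient MME can support a conclusion about postoperative consumption but not about overall consumption. The uncounted tablet is between 25% and 100% of a study patient's Dsuvia. The conclusion rests on reading inpatient as the period after the PACU. It is confined to a secondary outcome.

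Two stronger readings are tempting, and the documents support neither.

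- *That the omission biases the comparison in favour of Dsuvia overall.* Leaving out the tablet, taken alone, does favour the study arm. The net direction also depends on the controls' intraoperative opioids, which are not given. The infusion might largely cancel against the sufentanil control group, or it might not.
- *That counting the tablet would cancel the saving reported in the cited historical-control study.* There, PACU MME was 8.1 in controls and 3.6 with Dsuvia, a difference of 4.5. A tablet worth 5 would turn 3.6 into 8.6. That sum has to treat the Background equivalence, printed for 30 mg, as applying to the 30 mcg tablet. It also assumes that the cited MME excludes the tablet, and it adds no intraoperative opioid to the controls. It is not an overall total and says nothing about this trial's data. The statement that 48.5% of that study's Dsuvia patients avoided opioids is likewise limited, in the Background itself, to the PACU.

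**What to change.** **Preferred.** Keep PACU plus inpatient MME, state that PACU Dsuvia is counted in it, and call it postoperative opioid consumption. Change overall to postoperative in the Purpose, in Hypothesis 2 and in the wording of the conclusion. This is an edit to the text and needs no new data.

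**If overall is kept.** Add a secondary total MME from the operating room to hospital discharge, defined in the same way in all three groups. It should count every Dsuvia tablet, including the operating-room one, together with boluses and infusions. Show it with and without the maintenance infusion, which may otherwise dominate the total. The cost is abstracting intraoperative opioids from at least 2 × 80 = 160 control records.

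**Downside.** The apparent saving may shrink once the tablet is counted.

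**A separate point that must be settled first.** The Background prints a morphine equivalence for 30 mg, while the Study Schema and the clinical protocol describe a 30 mcg tablet. These must be reconciled before any MME conversion is fixed. Both options depend on this, because each counts sublingual Dsuvia in MME.

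### Study patients pass through an undefined surgeon judgement that has no stated counterpart for the historical controls, and the shared ten covariates may not fully adjust for it

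*Combined protocol and SAP*

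**What the plan says.** Recruitment is described under Detailed Clinical Protocol, Preoperative. The surgeon introduces the study and sees the patient, and then: "At this visit, the surgeons will identify any patients that may benefit from Dsuvia". The names go to an investigator. Next comes "The investigator will subsequently review their eligibility and inclusion criteria", and then "If the subject continues to meet all the criteria, the investigator will explain the study with the patient". What makes a patient likely to benefit is not defined. No other route into the study arm, no consecutive enrolment and no screening log are described.

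Methods defines the two control arms by the intraoperative infusion received (remifentanil or sufentanil) and by the absence of Dsuvia. One set of inclusion and exclusion criteria follows the description of all three arms. Sample Size/Statistical analysis adds the number: "inclusion of at least 80 patients in each retrospective control group". The document names no chart source, no calendar window and no rule for choosing among eligible charts.

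The same section lists the adjustment covariates: "age, sex, BMI, ASA class, surgical invasiveness tier, reoperation, history of anxiety, anxiolytic use, history of depression, and antidepressant use". The propensity score is "conditional upon the aforementioned covariates included in the multivariable outcome model", so the two models share one list. The stated safeguard is: "Doubly robust estimation will allow for unbiased treatment effect estimates even if one of the two models" is wrongly specified. For study patients, "The baseline NRS score will be recorded" before premedication, but this score is in neither model.

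**The concern.** The design is openly observational, so the primary contrast depends on the arms being comparable after adjustment. A surgeon's view of who may benefit can carry prognostic information, such as expected pain, anticipated difficulty of the operation or how the patient is coping. If that view helps decide who enters the study arm and nothing similar shapes the control groups, the arms can differ in ways the covariates do not record.

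Double robustness protects against a wrong form for one of the two models, provided the factors that matter are measured and the other model is right. It does not protect against a prognostic factor left out of both. With a shared covariate list, a factor not captured by the list is left out of both.

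The direction is open. If surgeons refer patients they expect to do well, the contrast favours Dsuvia. If they refer those they expect to have more pain, a real benefit could be hidden. Without a screening log and a stated control rule, a reader could not tell which applies or how strongly.

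**Working it through.** **Inputs from Sample Size/Statistical analysis.** SD 2.5 NRS points; 30 study patients; at least 80 per control group; two-sided alpha 0.025 per comparison; difference of interest 2 points; stated power at least 80%.

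**The plan's own figure.**
- SE = 2.5 × √(1/30 + 1/80) = 2.5 × 0.2141 = 0.535.
- Critical z for two-sided 0.025 = 2.241.
- Power = Φ(2/0.535 − 2.241) = Φ(3.737 − 2.241) = 93.3% (92.7% with the noncentral t on 108 degrees of freedom).

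The stated power therefore holds, and the sample size is not in dispute.

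**How much residual bias matters.** With no true effect and a bias b left after adjustment, the per-comparison type I error is Φ(b/SE − 2.241) + Φ(−b/SE − 2.241). Setting this to 5%, twice the nominal 2.5%, gives the tipping point. The plan does not say how far weighting will widen the SE, so inflations of 25% and 50% are assumed alongside none.

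| SE | Bias at which the error reaches 5% | As a share of 2 points |
|---|---|---|
| 0.535 (unweighted) | 0.31 | 15% |
| 0.669 (+25%, assumed) | 0.38 | 19% |
| 0.803 (+50%, assumed) | 0.46 | 23% |

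**What selection could produce.** The documents give no figure, so this part is assumption throughout. Take a yes/no factor present in half of patients, unrelated to the measured covariates, that raises NRS by 1 or 2 points and makes selection into the study arm 2 or 4 times as likely. Its prevalence in the study arm would be about 2/3 or 4/5 against 1/2 in controls, a gap of about 0.17 or 0.30. Bias is roughly effect × gap. A doubly robust simulation (1,500 replicates per scenario, 30 versus 80, no drug effect, both models using one measured covariate and neither using the factor) gave:

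| Factor's effect on NRS | Selection ratio 1 | Ratio 2 | Ratio 4 |
|---|---|---|---|
| 1 point | 0.00 | 0.16 | 0.31 |
| 2 points | 0.02 | 0.33 | 0.60 |

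With no selection the estimator is centred on zero. With selection, it keeps almost the whole bias that the simple product predicts. At the unweighted SE, biases of 0.16 and 0.60 points give type I errors of 3.2% and 13.2%. With the SE inflated by 50% they give 2.8% and 6.9%.

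If the same biases ran against Dsuvia and the true effect were 2 points, power at the unweighted SE would be Φ((2 − 0.16)/0.535 − 2.241) = 88% and Φ((2 − 0.60)/0.535 − 2.241) = 65%, instead of 93%.

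**Room to adjust further.** The propensity model has 30 study patients for ten covariates, or 30/10 = 3 per covariate, and fewer if ASA class or invasiveness tier needs more than one term. Adding many covariates later is a poor remedy.

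**Side check on the source population.** Inclusion criteria limits surgery to one to three levels; the heading line of IV. STUDY SCHEMA has one or more levels with no upper limit. The two must be reconciled before the same pool can be applied to every arm.

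**The case against.** The surgeon step may select very little. The words in "If the subject continues to meet all the criteria, the investigator will explain the study with the patient" can be read to mean that the written criteria had already been applied at the surgeon's visit. Purpose also describes this population as one that routinely has moderate to severe acute pain, so on the protocol's own framing nearly every eligible patient might benefit. Both readings are fair. They make a weak filter plausible, but the text does not settle it.

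A reader might infer that the controls have no selection rule at all. The documents do not support that. The eligibility criteria come after all three arms have been introduced and are not limited to the study arm, so they most likely cover the controls. What is missing is narrower: a sentence saying so, and the source, window and sampling rule.

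It can also be said that the covariates already capture much of the judgement. ASA class, invasiveness tier, reoperation, anxiety and depression could well do so jointly, and the simulated biases, which assume no capture, would shrink accordingly. The documents do not allow the captured share to be estimated in either direction.

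Finally, the bias sizes are assumed, and the same arithmetic would apply to any unmeasured confounder in an observational comparison. That stands. The figures show how sensitive the test is, not how large the bias will be.

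**Conclusion.** The point holds as a design weakness that is cheap to reduce. An undefined judgement precedes the eligibility review on the only recruitment route described, no counterpart is described for the controls, and the safeguard the plan relies on does not cover a factor absent from both models. It should be fixed; confidence is medium, because the filter may prove weak.

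Size: the per-comparison error doubles to 5% at a residual bias of 0.31 to 0.46 points, depending on an assumed 0% to 50% inflation of the SE. That is 15% to 23% of the 2-point difference. Assumed biases of 0.16 to 0.60 points correspond to errors of 3.2% to 13.2% at the unweighted SE. All of this rests on the plan's SD and group sizes and a normal approximation.

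A reader might go further and conclude that the result will be biased towards Dsuvia, or that the type I error is some particular inflated value. Neither follows: the direction is open, and no bias size can be derived from the documents.

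**What to change.** 1. Replace the surgeon's identification step with screening of all consecutive patients on the participating surgeons' lists against the written criteria. Keep a log of those eligible, approached and consented. If the step was only ever meant as the written criteria, say so.
2. Take controls as all consecutive charts that meet the same criteria within a stated calendar window, and name the source.
3. Reconcile the two statements on number of levels and apply one wording to all three arms.
4. State whether control charts hold a preoperative NRS. If they do, report it by arm and add it to both models in a sensitivity analysis only, given the thin propensity model. If they do not, state the limitation.

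The cost is amendment wording, a log with a named keeper (the research assistant is still to be appointed), slightly more screening work and, where charts allow, one extra analysis. The protection is partial: consent continues to filter the study arm and not the controls, and a log documents selection without removing it.
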